4.1 Enrolment/screening period

Screening procedures will be performed according to the Study Plan for Part A (Table 1).

At screening, consenting patients are assessed to ensure that they meet eligibility criteria. Patients who do not meet these criteria must not be enrolled in the study.

Patients will be considered to be in screening period until all Visit 1 assessments are completed and eligibility is confirmed. Patients will be considered enrolled and in the treatment period once IP has been initiated.

The study procedures carried out during this period include: physical examination, vital signs (blood pressure, pulse rate, body temperature), ECG, Echo/MUGA, weight, height, ophthalmic examination, demographics, concomitant medication, medical/surgical history, smoking history, blood samples for haematology, clinical chemistry and coagulation, hepatitis B and hepatitis C status, urinalysis, pregnancy test, diagnosis and assessment of the disease for which the IP is being tested (ECOG performance status).

4.2 Treatment period

Descriptions of the procedures for this period are included in the Study Plans for Part A ([Table 1](#)) and for Part B ([Table 2](#)).

The timing of PK blood samples for AZD9291 and rifampicin is detailed in [Table 3](#).

It is important that PK sampling occurs as close as possible to the scheduled time. In order to achieve this, other assessments scheduled at the same time may be initiated prior to the timepoint. The sequence to be followed at a particular post-dose timepoint is:

1. ECGs
2. Vital signs
3. PK blood sample (at scheduled time)
4. Any other assessments

Pre-dose vital signs assessments should be collected within 60 minutes prior to dosing.

A 30-minute window will be allowed for PK samples taken at pre-dose (sample must be taken prior to dose), a 5-minute window will be allowed for post-dose samples up to 1 hour; a 10-minute window for samples taken at 2 to 10 hours post-dose and a 1-hour window for samples taken from 12 hours post-dose onwards. The window for trough samples is ± 1 day; however, on a given day the trough sample must be collected prior to the next dose of IP.

All Day -1 procedures must be performed in the clinic on Day -1 or pre-dose on Day 1; patients may be admitted on Day 1 if the Day -1 activities (see [Table 1](#)) can be completed on the same day. If the patient has been screened within 48 hours of Day 1, safety laboratory tests (haematology, coagulation, biochemistry and urinalysis) do not need to be repeated.

Part A

All treatments (AZD9291 and rifampicin) will be administered with the patient fasted from at least 2 hours before dosing to at least 2 hours after dosing. The study treatments should be swallowed whole with approximately 240 mL of water, and not chewed, crushed, dissolved or divided. Water is allowed as desired except for 1 hour before and after AZD9291 administration on Days 28, 49, and 77. There are no restrictions for water intake on any other study days.

Period 1: On Day 1, patients will attend the clinic and receive a single oral dose of AZD9291 80 mg in the morning, having been fasted from at least 2 hours before dosing to 2 hours post-dose. They will continue to take AZD9291 80 mg once daily, fasted, on an outpatient basis from Day 2 to 27. Patients will return to the clinic on an outpatient basis for PK assessments on Days 7, 14 and 21 prior to taking their daily AZD9291 dose. The AZD9291 dose may be taken in the clinic after collection of the pre-dose PK sample. There is a ± 1 day

window for the outpatient visits. Patients will check into the clinic on the morning of Day 28 (± 1 day) prior to taking their daily AZD9291 regimen. On the morning of Day 28, patients will receive a single oral dose of AZD9291 80 mg, fasted. Patients will remain resident until 24 hours after the dose of AZD9291, during which time PK blood samples and other safety information will be collected.

Period 2: Treatment Period 2 will start 28 days after the first dose of AZD9291 (Day 29 [± 1 day]). On Day 29, patients will commence daily doses of rifampicin (600 mg once daily) and continue daily doses of AZD9291 80 mg once daily for 3 weeks. Rifampicin doses should be taken fasted along with AZD9291. The Day 29 AZD9291 and rifampicin regimen may be taken in the clinic. Patients will then continue to take AZD9291 80 mg once daily and rifampicin 600 mg daily, fasted, on an outpatient basis from Day 30 to 48. Patients will return to the clinic on an outpatient basis for PK assessments on Days 35 and 42 prior to taking their daily AZD9291 and rifampicin dose. The AZD9291 plus rifampicin dose may be taken in the clinic after collection of the pre-dose PK sample. There is a ± 1 day window for the outpatient visits. Patients will check into the clinic on the morning of Day 49 (± 1 day) prior to taking their daily AZD9291/rifampicin regimen. On the morning of Day 49, patients will receive a single oral dose of AZD9291 80 mg taken concomitantly with rifampicin 600 mg, fasted. They will remain resident until 24 hours after the dose of AZD9291, during which time PK blood samples and safety information will be collected.

Period 3: Treatment Period 3 will start 21 days after the first dose of rifampicin (Day 50). Patients will then continue to take AZD9291 80 mg daily, fasted, on an outpatient basis from Day 50 to 77. The Day 50 AZD9291 regimen may be taken in the clinic. Patients will return to the clinic on an outpatient basis for PK assessments on Days 56, 63 and 70 prior to taking their daily AZD9291 dose. The AZD9291 dose may be taken in the clinic after collection of the pre-dose PK sample. There is a ± 1 day window for the outpatient visits. Patients will check into the clinic on the morning of Day 77 (± 1 day) prior to taking their daily AZD9291 dose. On the morning of Day 77, patients will receive a single oral dose of AZD9291 80 mg in the morning, fasted. Patients will remain resident until 24 hours after the dose of AZD9291, during which time PK blood samples and other safety information will be collected.

Part B and continued access

AZD9291 can be taken with or without food during Part B and continued access.

On completion of Part A, patients may continue to take AZD9291 tablets (Part B) if they and the Investigator agree that this is appropriate. Patients should start Part B immediately (ie, 24 hours) after the last dose received in Part A (Day 78 after the 24-hour sample collection). Patients will have weekly clinic visits for the first 4 weeks; thereafter visits will be every 4 weeks. Safety assessments as detailed in [Table 2](#) will be collected and there will be no formal evaluation of efficacy. Patients' medical/oncological care will be according to local clinical practice. Part B will be of approximately 12 months' duration from the date the last patient enters this part of the study.

During and after Part B, patients may continue to take AZD9291, if they and the Investigator deem it appropriate, until such time as the Investigator believes they are no longer deriving clinical benefit or they stop taking AZD9291 for any other reason. After the end of Part B (approximately 12 months after the last patient entered Part B), patients will be seen as per their normal routine clinical schedule. After Part B is completed, patients may continue to receive AZD9291 as part of continued access (see Section 7.8). No further data will be recorded, other than the data specified in Section 7.8.

4.3 Follow-up period

Patients will return to the clinic for follow-up assessments 30 days (± 7 days) after their last dose, regardless of whether the last dose was in Part A or Part B. Follow-up assessments for Part A are detailed in Table 1; follow-up assessments for Part B are detailed in Table 2.

If the patient's last dose of AZD9291 is in the continued access phase (after Part B), the patient should be contacted 30 days after their last dose of AZD9291 to follow up any existing SAEs and monitor for new SAEs that may be related to IP.

5. STUDY ASSESSMENTS

The Inform Web Based Data Capture (WBDC) system will be used for data collection and query handling. The Investigator will ensure that data are recorded on the eCRFs as specified in the study protocol and in accordance with the instructions provided.

The Investigator ensures the accuracy, completeness, and timeliness of the data recorded and of the provision of answers to data queries according to the Clinical Study Agreement. The Investigator will sign the completed eCRFs. A copy of the completed eCRFs will be archived at the study site.

5.1 Efficacy assessments (not applicable)

5.2 Safety assessments

5.2.1 Laboratory safety assessments

Blood and urine samples for determination of clinical chemistry, haematology, coagulation, and urinalysis will be taken at the times indicated in the Study Plans (Table 1 for Part A, and Table 2 for Part B). If screening is undertaken within 48 hours of Day 1, safety laboratory tests do not need to be repeated.

Additional safety samples may be collected if clinically indicated at the discretion of the Investigator. The date, time of collection and results (values, units and reference ranges) will be recorded on the appropriate eCRF.

The haematology, clinical chemistry, coagulation, and urinalysis will be performed at a local laboratory at or near to the Investigative site. Sample tubes and sample sizes may vary depending on laboratory method used and routine practice at the site.

The following laboratory variables will be measured:

Table 4 Laboratory safety variables

Clinical chemistry (2.7 mL sample)	Haematology (2.7 mL sample)
Serum (S)/Plasma (P)-Albumin	Blood (B)-Haemoglobin
S/P-ALT	B-Leukocyte
S/P-AST	B-Haematocrit
S/P-Alkaline phosphatase	B-Red blood cell count
S/P-Bilirubin, total	B-Absolute leukocyte differential count:
S/P-Calcium, total	Neutrophils
S/P-Creatinine	Lymphocytes
S/P-Glucose	Monocytes
S/P-Lactate dehydrogenase	Basophils
S/P-Magnesium	Eosinophils
S/P-Potassium	B-Platelet count
S/P-Sodium	B-Reticulocytes
S/P-Urea nitrogen or Blood urea nitrogen	Urinalysis (dipstick)^a
Coagulation^b (1.8 mL sample)	U-Glucose
B-Activated partial thromboplastin time	U-Protein
B-International normalised ratio	U-Blood
Serology screen (1.8 mL sample)	Pregnancy tests
Hepatitis B and C (HBV, HCV) ^c	Blood or urine

^a Microscopic analysis should be performed by the hospital's local laboratory if required.

^b For patients taking warfarin see Section 7.7.

^c HBV DNA and HCV RNA if required to confirm active disease.

ALT alanine aminotransferase; AST aspartate aminotransferase; HBV hepatitis B virus; HCV hepatitis C virus

Pre-menopausal women of childbearing potential must have a negative urine or serum pregnancy test within 28 days prior to starting study treatment, and a confirmatory test before treatment at Visit 1. In the event of suspected pregnancy during the study, the test should be repeated and, if positive, the patient discontinued from study treatment immediately. The pregnancy test will be repeated at follow-up 30 (±7) days after last dose of study medication (in Part A or Part B as appropriate). Tests will be performed by the hospital's local laboratory. If results are positive, the patient is ineligible/must be discontinued from the study.

Routine urinalysis should be performed if clinically indicated. Microscopic analysis should be performed by the hospital's local laboratory if required.

Any clinically significant abnormal laboratory values should be repeated as clinically indicated and recorded on the eCRF.

NB. In case a patient shows an AST **or** ALT ≥ 3 x ULN **or** total bilirubin ≥ 2 x ULN please refer to [Appendix E](#) ‘Actions required in cases of combined increase of Aminotransferase and Total Bilirubin – Hy’s Law’, for further instructions.

The Investigator should make an assessment of the available results with regard to clinically relevant abnormalities. The laboratory results should be signed and dated and retained at centre as source data for laboratory variables. For information on how AEs based on laboratory tests should be recorded and reported, see Section 6.3.

5.2.2 Volume of blood

The maximum volumes of blood that will be taken for any given patient for the purposes of the study are as follows:

- Part A: 219.2 mL (see Table 5)
- Part B: 91.8 mL (see [Table 6](#)).

Table 5 Blood sample volumes (per patient) – Part A

		Sample Volume (mL)	Number of Samples					Total Volume (mL)
			Screening	Period 1	Period 2	Period 3	FU	
Safety	Clinical chemistry	2.7	1	5	3	4	1	37.8
	Haematology	2.7	1	5	3	4	1	37.8
Coagulation	aPTT/INR	1.8	1	0	0	0	0	1.8
PK	AZD9291 and metabolites	2.0	0	13	12	13	0	76.0
	Rifampicin	2.0	0	0	11	1	0	24.0
	4 β -hydroxy-cholesterol	5.0	0	3	1	2	0	30.0
Serology	HBV/HCV	1.8	1	0	0	0	0	1.8
PG	Pharmacogenetics sample	10.0	0	1	0	0	0	10.0
Total Volume (mL)			9.0	78.0	67.2	59.6	5.4	219.2

Note: Table is for guidance. Exact blood volumes may differ depending on local requirements.

aPTT activated partial thromboplastin time; FU follow-up; HBV hepatitis B; HCV hepatitis C; INR international normalised ratio; PG pharmacogenetics; PK pharmacokinetics

Table 6 Blood sample volumes (per patient) – Part B

		Sample Volume (mL)	Number of Samples			Total Volume (mL)
			Weekly visits	Monthly visits	Follow-up ^a	
Safety	Clinical chemistry	2.7	4	12	1	29.7
	Haematology	2.7	4	12	1	29.7
Total Volume (mL)			21.6	64.8	5.4	91.8

Note: Table is for guidance. Exact blood volumes may differ depending on local requirements. Number of samples is based on a patient being in Part B for 12 months.

^a Applicable for any patient who permanently discontinues AZD9291 during Part B of the study.

5.2.3 Physical examination

A physical examination will be performed at screening, Day -1 of Part A, at every visit during Part B and at follow-up. Physical examinations conducted during Part B will not be captured on the eCRF.

The physical examination will include a whole body inspection as follows: general appearance, skin, head and neck, lymph nodes, thyroid, musculoskeletal/extremities, cardiovascular, respiratory, abdomen, neurological, genital/rectal, breast.

If new or aggravated physical findings imply deterioration compared with baseline, the finding should be reported as an AE (Section 6.3.6).

5.2.4 ECG

5.2.4.1 Resting 12-lead ECG

A 12-lead safety ECG (paper ECG printout of 10 seconds for Investigator review) will be taken at the times specified in Table 1 and Table 2.

For each timepoint three ECG recordings should be taken within an approximate 5 minute period. Additional ECGs may be taken at any other time the Investigator deems necessary for safety during the dosing period. The patients will rest for at least 10 minutes before the start of each recording and they must be in the same supine body position (maximum 30 degrees flexion in the hip and feet not in contact with the footboard) at each recording timepoint during all visits.

The Investigator will judge the overall interpretation as normal or abnormal. If abnormal, it will be decided as to whether or not the abnormality is clinically significant or not clinically significant. The paper copy of each ECG reading will be retained with the patient's completed source documents. Only overall evaluation (normal/abnormal) will be recorded in the eCRF. If there is a clinically significant abnormal ECG findings during the treatment period, this should be recorded on the AE eCRF, according to standard AE collection and reporting processes (see Section 6.3.6).

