7. Spinal cord compression or brain metastases unless asymptomatic, stable and not requiring steroids for at least 4 weeks prior to start of study treatment.
8. Any evidence of severe or uncontrolled systemic diseases, including uncontrolled hypertension and active bleeding diatheses, which in the Investigator's opinion makes it undesirable for the patient to participate in the study or which would jeopardise compliance with the protocol, or active infection including hepatitis B,

hepatitis C and human immunodeficiency virus (HIV). Screening for chronic conditions is not required.

9. Inadequate bone marrow reserve or organ function as demonstrated by any of the following laboratory values:
 - Absolute neutrophil count $<1.5 \times 10^9/L$
 - Platelet count $<100 \times 10^9/L$
 - Haemoglobin $<90 \text{ g/L}$
 - Alanine aminotransferase (ALT) >2.5 times the upper limit of normal (ULN) if no demonstrable liver metastases or >5 times ULN in the presence of liver metastases
 - Aspartate aminotransferase (AST) >2.5 times ULN if no demonstrable liver metastases or >5 times ULN in the presence of liver metastases
 - Total bilirubin >1.5 times ULN if no liver metastases or >3 times ULN in the presence of documented Gilbert's Syndrome (unconjugated hyperbilirubinaemia) or liver metastases
 - Creatinine >1.5 times ULN concurrent with creatinine clearance $<50 \text{ ml/min}$ (measured or calculated by Cockcroft and Gault equation); confirmation of creatinine clearance is only required when creatinine is >1.5 times ULN.
10. Any of the following cardiac criteria:
 - Mean resting corrected QT interval corrected for heart rate using Fridericia's correction factor (QTcF) $>470 \text{ msec}$ obtained from 3 electrocardiograms (ECGs)
 - Any clinically important abnormalities in rhythm, conduction or morphology of resting ECG eg, complete left bundle branch block, third degree heart block, second degree heart block, PR interval $>250 \text{ msec}$
 - Any factors that increase the risk of QTc prolongation or risk of arrhythmic events such as heart failure, hypokalaemia, congenital long QT syndrome, family history of long QT syndrome or unexplained sudden death under 40 years of age or any concomitant medication known to prolong the QT interval ([Appendix H](#)).
11. Patients unable to swallow orally administered medication or patients with gastrointestinal disorders or significant gastrointestinal resection likely to interfere with the absorption of AZD9291.

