^b Day 1 is the day of dosing; Day -1 is the day before dosing. All Day -1 procedures must be performed on Day -1 or pre-dose on Day 1 provided the results are reviewed before dosing. If the patient has been screened within 48 hours of Day 1, safety laboratory tests (haematology, coagulation, biochemistry and urinalysis) do not need to be repeated.

^c Patients will check into the clinic on the morning of Day 28, Day 49 and Day 77 and be prepared to stay overnight for 24 hours serial blood collections and safety assessments.

^d Height to be assessed at Screening only. Weight to be assessed at all timepoints; the same weighing scales should be used at each visit. For height and weight, indoor clothing may be worn but shoes should be removed.

^e Supine BP and pulse will be measured pre-dose, using a semi automatic BP recording device with an appropriate cuff size after the patient has been resting in bed for 10 minutes. For ECG, patients will rest at least 10 minutes before the start of each ECG recording and they must be in the same supine (maximum 30 degrees flexion in the hip and feet not in contact with the footboard) body position at each recording timepoint. On Days 28, 49 and 77, assessments will be performed pre-dose and at 3, 6 and 12 hours post-dose.

- ^f For haematology and clinical chemistry tests, see [Table 4](#). Coagulation (aPTT and INR) will be performed at Screening and if clinically indicated. For patients taking warfarin reference Section [7.7](#).
- ^g Protein, blood and glucose; microscopic analysis is to be performed if required.
- ^h Pre-menopausal women of childbearing potential must have a negative urine or serum pregnancy test within 28 days prior to starting treatment and a confirmatory test before treatment at Visit 1. In the event of suspected pregnancy during the study, the test should be repeated and, if positive, the patient discontinued from study treatment immediately. Pregnancy test will be repeated at the follow-up 30 (± 7) days after last dose of study medication.
- ⁱ Patients will be invited to participate in optional genetic research. The patient must provide separate informed consent. If the patient declines to consent to the optional genetic research, this will not exclude the patient from participating in any other aspect of the study.

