6.7 Management of IP-related toxicities

Patients who have IP-related toxicities requiring dose interruption or dose reduction may be discontinued from Part A and entered into Part B following discussion with an AstraZeneca representative.

The following text is guidance for investigators who treat patients with AZD9291 in Part B and during continued access.

If a patient experiences a CTCAE Grade 3 or higher and/or unacceptable toxicity (any grade) not attributable to the disease or disease-related processes under investigation, where the Investigator considers the AE of concern to be specifically associated with AZD9291, dosing will be interrupted and supportive therapy administered as required in accordance with local practice/guidelines.

If dose reduction is necessary, then the dose of AZD9291 should be reduced to 40 mg taken once daily. Patients who reduce to the 40 mg dose must remain on the 40 mg dose for the remainder of the study.

Dose interruption and reduction guidelines are provided in [Table 7](#).

Table 7 AZD9291 dose adjustment information for adverse reactions

Target organ	Adverse reaction	Dose modification
Pulmonary	ILD/pneumonitis	Permanently discontinue AZD9291
Ocular	Corneal ulceration	Permanently discontinue AZD9291
Cardiac	QTc interval >500 msec on at least 2 separate ECGs	Withhold AZD9291 until QTc interval is <481 msec or recovery to baseline if baseline QTc is ≥481 msec, then restart at the reduced dose (40 mg)
	QTc interval prolongation with signs/symptoms of serious arrhythmia	Permanently discontinue AZD9291
Other	Grade 3 or higher adverse reaction	Withhold AZD9291 for up to 3 weeks
	If Grade 3 or higher adverse reaction improves to Grade 0-2 after withholding AZD9291 for up to 3 weeks	AZD9291 may be restarted at the same dose (80 mg) or a lower dose (40 mg)
	Grade 3 or higher adverse reaction that does not improve to Grade 0-2 after withholding AZD9291 for up to 3 weeks	Permanently discontinue AZD9291

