8.5.3 Demographic and safety analyses

Data for Parts A and Part B will be analysed separately.

For qualitative demographic and safety variables, the population size (N for sample size and n for available data) and the percentage (of available data) for each class of the variable will be presented. Quantitative variables will be summarised using descriptive statistics, including n, mean, SD, median, minimum, and maximum values. Where appropriate, assessments will be summarised by visit. All data will be summarised and listed appropriately.

The number of patients screened and included in the safety analysis set will be summarised. Demographic and baseline characteristics will be summarised and listed for the safety analysis set.

Treatment duration will be summarised. Treatment duration is based on the dates of first and last dose of any study treatment.

Study day will be calculated as follows:

- Days prior to first dose: Study day=date – first dose date.
- Days on or after first dose: Study day=date – first dose date+1.

Where day is missing from the date, but is required in the calculation of time to informed consent, day will be imputed as 01, ie, 1st of the month. Otherwise no imputations will be made for any missing data, unless agreed by the study team.

Safety profiles will be assessed in terms of AEs, vital signs (including blood pressure and pulse rate), ECG, laboratory data (clinical chemistry, haematology and urinalysis) and physical examinations.

Appropriate summaries of AEs, laboratory data, vital signs, and ECGs will be produced. Adverse events will be summarised separately for Parts A and B of the study. Laboratory data, vital signs, physical examinations, temperature, and ECGs will be summarised for

Parts A and B. Summaries will be presented for scheduled visits only. Any unscheduled assessments will be listed. The baseline value is defined as the latest result obtained prior to the start of study treatment.

The number of patients experiencing AEs following administration of AZD9291 and rifampicin, as well as the number of AEs experienced, will be summarised. Adverse events will be classified using the Medical Dictionary for Regulatory Activities (MedDRA) system of nomenclature (preferred term and system organ class). Adverse events reported before administration of AZD9291 will be listed only and be referred to as “pre-treatment”. Treatment emergence will be defined for each part of the study (A and B).

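### Triplicate ECGs are scheduled at PK-matched hours, but the eCRF takes only normal/abnormal, so the planned ECG summaries cannot include QTcF

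*Protocol*

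**What the plan says.** Section 5.2.4.1 describes a safety ECG on paper for the investigator's review. It requires replication: "For each timepoint three ECG recordings should be taken within an approximate 5 minute period". The investigator calls each ECG normal or abnormal and, if abnormal, judges its clinical significance. On capture it says "Only overall evaluation (normal/abnormal) will be recorded in the eCRF". Clinically significant abnormal findings on treatment also go to the AE form. On storage, "The paper copy of each ECG reading will be retained with the" patient's source documents.

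Table 1 places ECGs at screening, on the three PK days and at follow-up for patients who leave without entering Part B. Its footnote e adds: "On Days 28, 49 and 77, assessments will be performed pre-dose and at 3, 6 and 12 hours post-dose". Table 2 adds ECGs at the four-weekly Part B visits and at follow-up.

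Standard 12-lead ECGs are a safety outcome for both parts (Sections 2.5 and 8.4). The Part A safety objective covers AZD9291 with and without rifampicin (Section 2.3). For analysis, Section 8.5.3 says "Appropriate summaries of AEs, laboratory data, vital signs, and ECGs will be produced".

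**The concern.** The schedule is built as if to measure an interval, while the database holds only a site judgement. Days 28, 49 and 77 are AZD9291 alone, with rifampicin and after rifampicin. The ECG hours coincide with PK sampling hours in Table 3, and Section 4.2 puts the ECG ahead of the PK draw at the same time point. Those are the conditions under which QTcF could be described by period alongside concentration.

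A normal/abnormal call hides any change within a category. A patient whose QTcF lengthens noticeably but is still read as normal shows nothing. What is at stake is the content of the cardiac safety tables: no QTcF level, no change and no count above a limit, from recordings the patients undergo anyway.

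**Working it through.** **How the protocol treats cardiac numbers elsewhere**

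- Eligibility (Section 3.2, criterion 10): a mean QTcF over three ECGs is compared with a numeric limit.
- Table 7 (Section 6.7, guidance for Part B and continued access): action depends on a "QTc interval >500 msec on at least 2 separate ECGs", and recovery is judged against numeric QTc values.
- LVEF (Section 5.2.5): the percentage itself goes on the eCRF.
- ECG (Section 5.2.4.1): only the overall evaluation goes on the eCRF. The protocol describes no digital capture, central reading or later extraction.

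So the protocol uses QTc as a number in its rules but gives it no place in the data described by Section 5.2.4.1.

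**What Section 8.5.3 can produce.** It can tabulate normal/abnormal by visit and period, plus any ECG-related AEs. It cannot tabulate QTcF, change from baseline or counts above a threshold. The missing item is the data value, so no analysis plan supplies it.

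**Volume in Part A.** The protocol gives no figure to reproduce. Inputs: 3 recordings per time point (Section 5.2.4.1), 4 time points on each of 3 PK days (Table 1, footnote e), 1 screening time point (Table 1), 38 enrolled and 30 evaluable patients (Section 8.2.1). Follow-up ECGs are left out because they apply only to patients who do not enter Part B.

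- Time points per patient: 1 + 3 × 4 = 13.
- Recordings per patient: 13 × 3 = 39.
- Upper limit with no withdrawals: 39 × 38 = 1,482 recordings, or 13 × 38 = 494 triplicate means.
- PK days only, 30 patients completing all three: 3 × 4 × 3 × 30 = 1,080 recordings, or 360 triplicate means.

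**Precision that numeric capture would give.** Take the mean within-patient QTcF difference between two PK days at the same hour, with n = 30. The 90% CI half-width is t(0.95, 29) × SD / √30, with t(0.95, 29) = 1.699. The protocol gives no SD for QTcF change, so the SD is an assumption:

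| Assumed SD of change (msec) | 90% CI half-width (msec) |
|---|---|
| 8 | 2.5 |
| 10 | 3.1 |
| 12 | 3.7 |
| 15 | 4.7 |

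**The case against.** The strongest reply is that the protocol does what it sets out to do. It calls this a safety ECG for investigator review, no objective or outcome names QTcF, and a normal/abnormal table satisfies the wording of Section 8.5.3. That stands: no stated analysis fails.

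Several further points also stand:

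- A reader might infer that QTcF is lost for good. It is not, because the tracings are kept as source documents and QTcF could be read from them later.
- A reader might infer that the QTcF exclusion cannot be checked. Section 9.2 provides source data verification with direct access to original records.
- A reader might apply Table 7 to the PK-day ECGs. Section 6.7 gives it as guidance for Part B and continued access only.
- Triplicates have local uses: averaging at eligibility, and confirming a prolonged QTc on separate ECGs.
- The only scheduled pre-treatment ECG is at screening, up to 28 days before dosing, so change from baseline is not time-matched.
- Section 8.2.1 assumes that rifampicin lowers AZD9291 exposure by 33%. The Day 49 contrast then looks at QTcF under lower exposure, in a sequential design without a concurrent control.

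The AE route answers the concern only in part. It depends on the site calling a finding clinically significant. It also refers to Section 6.3.6, which limits AE reporting of deterioration in protocol-mandated parameters to events that are serious or lead to discontinuation.

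These points limit the use of QTcF summaries. They do not explain why a value used in the protocol's own rules, from recordings taken at PK-matched hours, is left out of the database.

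**Conclusion.** The point holds as a cheap improvement, not as a broken analysis. Under Section 5.2.4.1 the ECG summaries for both parts are confined to normal/abnormal categories, and no QTcF value, change or outlier can come from the study database as specified. The primary PK analysis is untouched.

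The documents do not support saying that QTcF can never be analysed or that the safety objective fails. The first overlooks the retained tracings, and the second assumes an endpoint the protocol does not set.

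The figure of 1,482 recordings is a ceiling that assumes no withdrawals, whereas Section 8.2.1 allows for about 20%. The half-width of 3.1 to 4.7 msec rests on an assumed SD of 10 to 15 msec and 30 patients with both readings. It measures precision only and does not address the screening baseline, the sequential design or local reading at about 16 sites.

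**What to change.** In Section 5.2.4.1, replace the normal/abnormal-only rule: at each scheduled ECG, enter heart rate or RR, QT and QTcF in the eCRF together with the overall evaluation. The mean of the triplicate is enough.

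In Section 8.5.3, add a descriptive QTcF summary by period and time point. It should give:

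- change from the screening value, labelled as not time-matched;
- within-patient differences at the same hour between Days 28, 49 and 77;
- the number of patients above the 500 msec limit already in Table 7.

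The cost is entry of 13 triplicate means per patient in Part A, up to 494 for 38 patients if none withdraw, and one extra table. In Part B, one triplicate mean per four-weekly visit adds about 12 per patient over 12 months on the visit count in Table 6, plus one at follow-up where it applies. No extra ECG or visit is needed.
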